## **7.2.4 Deviations**

A protocol deviation is any unapproved discrepancy from a protocol research plan or Good Clinical Practice (GCP) guidelines, except where necessary to eliminate an immediate hazard to trial subjects.

### **7.2.4.1 Documenting and Reporting Deviations**

#### **Serious or Major Deviations**

Research staff should promptly report serious or major deviations, or those that affect participant eligibility, informed consent, or protocol endpoints; and/or any deviation that could potentially result in harm to participants. These should be reported within 24 hours of the deviation or of learning of the deviation, by submitting as necessary to the Stanford IRB via ‘eProtocol’, and then entering them into OnCore. The OnCore record should include the following:

- description of the deviation,
- corrective action taken,
- a statement whether the patient was harmed or could have been potentially harmed by the deviation, and
- whether the deviation was reported to the Stanford IRB.

Stanford research staff should also be immediately notified of the deviation, via email to [name], copying the study Research Nurse or Research Coordinator with subject line: “SECURE: SHORT FOX STUDY Major Deviation.” A Case Report Form (CRF) describing the event is required and could be generated from the OnCore entry (as a pdf or report) and attached to the email.

Stanford DSMC reviews deviations in OnCore to ensure completeness of the deviation report and ensure the safety of trial participants. The DSMC may request corrective action and/or prompt reporting to Stanford IRB. If reporting to Stanford IRB is required, Stanford’s research staff (Study Nurse or Coordinator) will assist with this by entering the deviation in ‘eProtocol’.

## **Minor Deviations**

Deviations not meeting the above criteria for major or ‘serious,’ or that do not have a significant effect on the subject’s rights, safety, or welfare, or on the integrity of the data -- e.g., conducting a protocol-required visit out of the protocol ‘window’ -- should be documented on the Deviation Log in Appendix V.

Deviations in OnCore or in Deviation logs should remain current at all time, and may be requested by Stanford for study renewals, audits, reports, analyses or other submissions for Stanford IRB, SRC, or DSMC.

## **8. CORRELATIVE/SPECIAL STUDIES**

### **8.1 ctDNA study**

#### **8.1.1 Collection of Specimen**

Blood will be drawn when patient is enrolled and registered on-study and during treatment for all patients and then at each follow-up along with the patient’s clinical labs among patients who pursue organ preservation (see Study Calendar). Tumor tissue and germline DNA will be sequenced to identify mutations to track in ctDNA blood samples. Therefore, whenever possible, tumor tissue will be collected, consisting of a punch from a paraffin embedded tissue block or several unstained slides. Samples will be sent to the [name] lab at Stanford for processing and analysis. Possible timepoints for requesting tumor tissue include: patient’s biopsy from time of diagnosis (this would take place retroactively), surgical resection specimens, and any additional biopsies obtained while on study.

#### **8.1.2 Shipping of Specimen**

N/A. Samples will be analyzed on-site at Stanford. In the event that the patient undergoes a biopsy at an outside institution, the research team may request that the outside site ship a tissue sample to Stanford for processing and analysis.

#### **8.1.3 Site Performing Correlative Studies**

ctDNA analyses will be performed on the collected blood specimens retrospectively at Stanford in the laboratory of [name] by his research staff using research-use only platforms (CAPP-Seq and PhasED-Seq). These analyses will NOT be used for eligibility or to inform treatment decisions and is for “after the fact” research analysis only.

#### **8.1.4 Coding of specimens for privacy protection**

At the time of enrollment each patient will be given a specific confidential identification number (IDN). Specimens will be stored under the patient’s IDN. The information can be shared with other investigators listed on this protocol. Study data will be maintained in password protected computer files (protected online database). Only research personnel will have access to this information.

## 9. STUDY CALENDAR

Activity	Pre-study (to be performed within 45 days of enrollment unless otherwise specified)	RT	Chemo	Primary Outcome Assessment 8 (+/- 4) weeks after Chemo (Time 0)	Follow-up after Time 0 g		
					Every 3 months	Months 3, 6, 12, 18, 24	Months 6, 12, 18, 24
Pregnancy Test a	X						
Biopsy within 180 days of enrollment	X			X e	X e		
Clinical Exam with DRE b	X		X d	X	X		
Procto/Sigmoidoscopy within 90 days of enrollment	X		X d	X	X		
CT chest/abdomen/pelvis c	X		X d	X			X
MRI pelvis	X		X d	X		X	
Labs-CBCD, CMP, CEA	X		X i	X			X
ECOG	X						
HRQOL	X j			X			X f
PET/MRI or FDG-PET c	X			X			
AE evaluation	X j	X	X	X L	X f		
ctDNA	X j	X k		X		X h	

aNegative pregnancy test by urine, for women non-post-menopausal as defined in Appendix.

bDRE may be deferred for clinical reasons, as determined by treating physician.

cMRI abdomen can substitute for CT abdomen/pelvis per physician discretion; PET imaging is *optional*. PET/MRI is preferred.

dRestaging after 8 (+/-4) weeks of chemotherapy. Procto/sigmoidoscopy and CT CAP can be omitted per physician discretion.

eIf biopsy is needed to rule out residual or progressive tumor, per the discretion of the surgeon

fAfter TME, patients will leave surveillance schedule but continue to receive HRQOLs, and be assessed for treatment-related AEs

gFollow-up appointments and activities 2 weeks before and 2 weeks after each timepoint are permitted, and may be completed virtually.

hAmong only those managed with organ preservation

iCEA does not need to be collected; pre-study CBCD, CMP may suffice for cycle 1 Day 1 chemo labs

jActivities to be done after enrollment and before treatment begins

kctDNA will be collected following completion of RT

LAn additional AE evaluation may be scheduled up to 3 months after completion of chemotherapy if needed

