### 1.2. Secondary Objectives

- To assess safety in all patients and local regrowth rate and other cancer specific outcomes (disease-free survival [DFS], colostomy-free survival and overall survival [OS]) among patients assigned to organ preservation approach.
- To assess longitudinal functional outcomes and health-related quality of life [HRQOL] of this organ preservation approach.

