#### **4.2.5 Follow-Up Schedule (Time 0 = assessment of primary outcome)**

Patients who achieve cCR and are candidates for organ preservation per multidisciplinary review will undergo surveillance per protocol schedule. If tumor shows near complete response, patient may continue to be observed until the next evaluable timepoint.

Additional scans and/or other tests may be performed and will be based on the clinical judgment of the treating physician.

Patients who are not candidates for organ preservation will proceed with TME. These patients will not proceed with the organ preservation surveillance schedule and instead be followed for cancer-specific outcomes (disease-free survival, colostomy-free survival and overall survival) per standard of care as directed by the treating physician. They will be assessed for AEs and health-related quality of life per Study Calendar.

For patients who achieve cCR and are on surveillance schedule, if suspicion of local regrowth (non-resolving residual abnormality that appears to increase in size or appears more suspicious in appearance or palpation, or imaging characteristics concerning for progression), patient will undergo a biopsy or a transanal full-thickness excision (TAE) if deemed appropriate to confirm. If biopsy is positive, patients will be managed per standard of care as directed by the treating physician.

Patients who pursue treatment for disease progression while on study will continue to be followed for OS, but discontinue routine AE assessment and QOLs, and follow-up with their treating physicians per standard of care.

After 2 years, all patients who initiated treatment on the protocol will be off study and followed for survival only. In general, patients who opt for organ preservation are recommended to continue to undergo surveillance years 3-5 as per below:

Recommend surveillance off study during years 3-5:

- Every 3-6 months
  - Exam and sigmoidoscopy
- Every 6 months
  - MRI pelvis and CT chest every 6 months

Follow-up PET/CTs or PET/MRI (preferred) are optional at any follow-up point, as per treating physician.

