### **12.5.2 Analysis Plan**

For the toxicity outcome, we will calculate the proportion of patients meeting our definition of toxicity. In addition, we will present the frequency and percent of other adverse events reported in the study.

Local regrowth rate will be calculated as the proportion of patients with local regrowth based on the secondary analysis population. The local regrowth rate and its 95% confidence interval will be calculated.

Disease-free survival is defined as the time from start of RT therapy to date of progression or death due to any cause. If a subject is not known to have progressed or died, then DFS will be censored at the latest date the subject was known to be alive or disease-free (on or before the cut-off date). The DFS distribution will be estimated using the Kaplan-Meier method, and the Kaplan-Meier curves, medians and 95% confidence intervals of the medians will be presented.

Colostomy-free survival distribution will be estimated using the Kaplan-Meier method, and the Kaplan-Meier curves, medians and 95% confidence intervals of the medians will be presented.

OS is defined as the time from start of RT therapy to date of death due to any cause. If a subject is not known to have died, then OS will be censored at the latest date the subject was known to be alive (on or before the study end date). The OS distribution will be estimated using the Kaplan-Meier method, and the Kaplan-Meier curves, medians and 95% confidence intervals of the medians will be presented.

For the HRQOL measures, we will calculate the mean and standard deviations of each of the individual indices at baseline and every 3 months during the duration of the study; we will graphically depict scores at each time point. In addition, we will calculate the difference of the QoL scores at the baseline, time of cCR, and last follow up date and report summary statistics.

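### Section 4.2.5 and Study Calendar footnote f can be read as giving opposite HRQOL and AE collection rules for a surveillance patient who has TME for local regrowth

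*Combined protocol and SAP*

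**What the plan says.** Two current passages govern what is collected after a patient leaves surveillance.

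- Section 4.2.5: "Patients who pursue treatment for disease progression while on study will continue to be followed for OS, but discontinue routine AE assessment and QOLs".
- Study Calendar, footnote f, attached to the HRQOL and AE cells after Time 0: "After TME, patients will leave surveillance schedule but continue to receive HRQOLs, and be assessed for treatment-related AEs".

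For patients who are not organ-preservation candidates and go to TME at Time 0, section 4.2.5 is clear: "They will be assessed for AEs and health-related quality of life per Study Calendar". For surveillance patients, the same section counts among the signs of suspected regrowth "imaging characteristics concerning for progression", and then says: "If biopsy is positive, patients will be managed per standard of care". It does not say which collection rule follows.

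Section 1.2 gives the objective: "To assess longitudinal functional outcomes and health-related quality of life [HRQOL] of this organ preservation approach". Section 12.5.1 sets the HRQOL population as everyone in the primary analysis. In section 12.5.2, "we will calculate the mean and standard deviations of each of the individual indices at baseline and every 3 months", and differences between baseline, time of cCR and last follow-up are summarised. No method is given for missing assessments.

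**The concern.** The case at issue is a patient with cCR who enters surveillance, has biopsy-proven regrowth and is treated with TME. Footnote f keeps HRQOL and treatment-related AE assessment going. The stop in 4.2.5 ends both if the TME counts as treatment for disease progression. The documents do not settle that question and give no order of precedence, so study staff could handle similar patients differently.

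If the stop is applied, the data are lost because organ preservation failed, which is informative dropout. The patient's earlier scores stay in the data, so the change to last follow-up would end at a score taken before rescue surgery. Sections 2.1 and 2.2.1 present avoidance of TME morbidity as a main reason for organ preservation. Leaving out the period after a failed attempt would therefore make the approach look better than it is, provided function is worse after TME. HRQOL not collected at the time cannot be recovered.

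**Working it through.** The plan states no figure on this point, so there is none to reproduce. The check compares the texts and then bounds the size.

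**1. Which rule applies to whom**

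- TME at Time 0: section 4.2.5 and footnote f both continue HRQOL and AE assessment. No conflict.
- Progression treated without TME, for example distant disease: the 4.2.5 stop applies and footnote f is not triggered. No conflict.
- Regrowth on surveillance, treated with TME: footnote f continues collection. The 4.2.5 stop applies only if regrowth is disease progression. Unresolved.

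Footnote f is not limited to TME at Time 0. Leaving the surveillance schedule fits a patient already on it, whereas Time 0 TME patients never start it. On the other side, 4.2.5 uses the word progression when describing suspected regrowth, and footnote e refers to ruling out residual or progressing tumour. Section 10.2 defines regrowth pathologically without saying whether it is progression.

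**2. How many patients**

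Inputs: 37 patients and the success boundary of 11 cCR (12.6.2); an alternative cCR rate of 0.40, so 0.40 × 37 = 14.8, about 15; regrowth of 2 of 71 = 2.8% in the first watch-and-wait series described in 2.2.1. The upper regrowth rate of 40% is an assumption, as is entry of every cCR patient into organ preservation.

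Affected = organ-preservation patients × regrowth rate.

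- Low: 11 × 0.028 = 0.3 (0.3/37, about 1% of all patients).
- High: 15 × 0.40 = 6.0 (6/37, about 16% of all patients).

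**3. Effect on a description of the organ-preservation group**

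The only functional figure in the documents is bowel dysfunction in 50–90% of patients after sphincter-sparing surgery (2.1), so prevalence stands in here for the planned index means. Assumptions: dysfunction d0 = 20% with an intact rectum; regrowth r = 20–30%, all treated by sphincter-sparing TME; d1 = 50–90% after TME.

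Full prevalence = (1 − r)·d0 + r·d1. If rescued patients stop contributing, the observed prevalence is d0 = 20%.

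- r = 20%, d1 = 50%: 0.8 × 0.20 + 0.2 × 0.50 = 26%.
- r = 30%, d1 = 90%: 0.7 × 0.20 + 0.3 × 0.90 = 41%.
- r = 2.8%: 0.972 × 0.20 + 0.028 × 0.50 = 20.8%, or 0.972 × 0.20 + 0.028 × 0.90 = 22.0%.

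**4. Effect on the population actually planned (12.5.1)**

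Direct-TME patients are included, with the same d1. With n organ-preservation patients and m = 37 − n direct-TME patients:

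Full = [n(1 − r)d0 + n·r·d1 + m·d1] / 37. Observed = [n(1 − r)d0 + m·d1] / (37 − n·r).

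- n = 15, m = 22, r = 20%, d1 = 50%: 14.9/37 = 40.3% against 13.4/34 = 39.4%. Gap 0.9 points.
- n = 15, m = 22, r = 30%, d1 = 90%: 25.95/37 = 70.1% against 21.9/32.5 = 67.4%. Gap 2.8 points.
- n = 11, m = 26, r = 20%, d1 = 50%: 15.86/37 = 42.9% against 14.76/34.8 = 42.4%. Gap about 0.5 points.
- n = 11, m = 26, r = 30%, d1 = 90%: 27.91/37 = 75.4% against 24.94/33.7 = 74.0%. Gap 1.4 points.

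**5. What is not touched**

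cCR is assessed at Time 0, before any regrowth on surveillance. The toxicity outcome runs only to 3 months after RT and chemotherapy (10.2), so most events after later rescue surgery fall outside it under either rule.

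**The case against.** The strongest reply is that there is no contradiction. Section 4.2.5 handles regrowth and progression in separate paragraphs, its mention of progression within the regrowth paragraph concerns suspicion before biopsy, and section 10.2 lists local regrowth and DFS as separate outcomes. Footnote f then reads as the specific rule for salvage TME. This is a reasonable reading and may be what was intended. What remains is that no passage says so. DFS counts documented progression without excluding regrowth, and the stop directly follows the regrowth paragraph.

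Three stronger readings are tempting and are not supported:

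- A reader might infer that later HRQOL means would come only from patients with an intact rectum. Section 12.5.1 includes all treated patients, and those sent directly to TME keep HRQOL. They would number 22 to 26 of 37 if 11 to 15 enter organ preservation.
- A reader might infer that the stop removes mainly failures of organ preservation. It covers treatment for any progression in any patient, and section 2.2.2 notes that distant metastasis can exceed 25%.
- A reader might infer that the safety endpoint is compromised. Its window closes at 3 months after treatment, and 4.2.5 stops routine AE assessment without mentioning SAE reporting.

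It is also fair to say that the synopsis and section 10.3 class HRQOL as exploratory, that its summaries are descriptive, and that no decision rule depends on it.

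**Conclusion.** The concern holds as an unresolved overlap between two collection rules, conditional on local regrowth being read as disease progression. Under that reading, about 0.3 to 6 of 11 to 15 organ-preservation patients would have no HRQOL after salvage TME; everything above the 2.8% regrowth rate is assumed. For a description of the organ-preservation group, which is what the section 1.2 objective concerns, the loss is informative. It flatters the approach if function is worse after TME, as section 2.1 suggests. Under the illustrative assumptions, dysfunction would be 26–41% with full data and 20% without the rescued patients, but only 20.8–22.0% with full data at 2.8% regrowth. The planned all-treated summaries would shift by about 0.5 to 3 percentage points. cCR and the sample size are unaffected, and the formal toxicity endpoint is largely unaffected. This is a worthwhile low-cost correction and does not threaten the trial's main conclusion.

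**What to change.** Reconcile the passages. In section 4.2.5, state that discontinuation of HRQOL and AE assessment does not apply to local regrowth managed by TME, and that these patients follow footnote f to month 24. Footnote f covers TME only; extending the exemption to transanal excision would be a new rule and is not proposed here.

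In section 12.5, keep the all-treated HRQOL population and add a descriptive HRQOL summary of all patients who entered organ preservation, including scores after rescue surgery.

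The cost is one sentence in each section, plus at most four further questionnaire sets per affected patient (months 6, 12, 18 and 24), which section 10.3 already allows by mail or portal, and the AE assessments that footnote f already foresees. The HRQOL summaries may look less favourable. The change concerns data collection only and alters no treatment.

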## **4. TREATMENT PLAN**

### **4.1 Pretreatment Studies**

The following will be completed after enrollment and before treatment begins

- HRQOL
- ctDNA
- AE Evaluation

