### **4.2 Treatment Schedule**

Study treatment will start within 30 days of eligibility determination.

Treatment will comprise 6 daily fractions of RT at 5 Gy per fraction followed 2-4 weeks later by approximately 4 months of chemotherapy.

Patients will be assessed for the primary outcome approximately 8 weeks (+/- 4 weeks) following completion of chemotherapy. Those who are not eligible for organ preservation will proceed with TME. All others will undergo organ preservation and surveillance for local regrowth for 2 years on protocol.

Treatment will be administered on an outpatient basis. No investigational or commercial agents or therapies other than those described may be administered with the intent to treat the patient's malignancy.

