### **6. DOSE MODIFICATIONS**

#### **6.1 Chemotherapy**

FOLFOXIRI, mFOLFIRINOX, FOLFOX, XELOX, and 5-FU and capecitabine during radiation are standard regimens that have been widely used for the treatment of colon and rectal cancer for more than a decade. Investigators should refer to package and inserts and local pharmacy practices for a complete list of potential toxicities and adhere to best practices. Treatment interruptions and modifications should be made at the discretion of the treating physician.

Subjects should be assessed for Adverse Events (AEs) once during each chemotherapy cycle, and AEs will be recorded. Serious Adverse Events (SAEs) should be reported promptly as according to the guidelines in this protocol.

Chemotherapy infusion records should be kept in the patient's study chart, either with the Medication Administration Record (MAR) or other clinic records which contain: Date of infusion, dose completed of each agent, modifications if any and reason for modification with supporting source documents as needed. Laboratory results prior to

infusion should also be supplied in the patient study chart, as well as the consultation note if the patient is seen by the treating physician.

Below are recommendations and **not** requirements; **modifications of chemotherapy dose and schedule are allowed as per clinical judgment of patient's treating medical oncologist.**

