### 7.2.3. Adverse Events (AEs) and AE Monitoring

An AE is defined as any untoward medical occurrence in a clinical investigation subject, regardless of causal attribution.

All AEs should be graded according to the NCI Common Terminology Criteria for Adverse Events, Version 5.0, available at <http://ctep.cancer.gov/reporting/ctc.html>.

AEs should be:

- Assessed at each consultation or follow-up visit,
- Assessed during each chemotherapy cycle (prior to infusion is acceptable), and
- Recorded in patient's medical chart using a Smartphase

Laboratory tests (CBC with differential and CMP) should also be obtained with each chemotherapy administration, and abnormal values also noted indicating AE Grade if applicable. For those patients who choose to receive chemotherapy locally, they will have a televisit, over a secure server, before every cycle where their Stanford treating physician will review and assess any adverse events.

AEs should also be:

- Reported to Stanford as per protocol guideline and upon request
- Noted in patient study charts and binder
- Entered into REDCap

AEs in REDCap should remain current and may be requested by Stanford for study renewals, audits, reports, analyses or other submissions for Stanford IRB, SRC, or DSMC. AEs may also be reviewed by members of the study monitoring group in meetings, audits, and/or site visits.

Updates and outcomes of AEs, SAEs, UPs, and deviations may take place during teleconferences or more frequently as needed.

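### Study Calendar footnote i accepts screening blood work, always drawn before radiation, as the cycle 1 day 1 chemotherapy labs and sets no age limit relative to cycle 1

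*Combined protocol and SAP*

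**What the plan says.** Section 7.2.3 gives the general rule: "Laboratory tests (CBC with differential and CMP) should also be obtained with each chemotherapy administration", with "abnormal values also noted indicating AE Grade if applicable". It names no exception for cycle 1.

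The labs row of the Study Calendar (section 9) carries footnote i in its chemotherapy cell. That footnote drops CEA during chemotherapy and adds that "pre-study CBCD, CMP may suffice for cycle 1 Day 1 chemo labs".

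The only window on the pre-study labs is 45 days, and it is tied to enrollment (eligibility criterion 6 and the calendar's pre-study column). For what follows, section 4.2 says "Study treatment will start within 30 days of eligibility determination" and "Treatment will comprise 6 daily fractions of RT at 5 Gy per fraction followed 2-4 weeks later by approximately 4 months of chemotherapy".

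Between screening and cycle 1 no further count or chemistry is scheduled. The radiation cell of the labs row is empty. Section 4.1 opens its list with "The following will be completed after enrollment and before treatment begins" and names quality of life, ctDNA and an adverse event evaluation only.

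**The concern.** A sample taken before radiation cannot show what radiation did to the counts. Section 7.1.5 lists leukopenia, lymphopenia and thrombocytopenia among the expected acute effects, and the next treatment is usually a triplet regimen. The recommended delays in section 6.1.1 depend on current neutrophils and platelets. The advice in section 6.1.2.7 (Liver Function Tests) to skip irinotecan at grade 2 bilirubin depends on current chemistry. A site that uses the allowance could give the first dose with neither.

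The two sections also point different ways. A site that works from section 7.2.3 draws labs at cycle 1, and a site that works from the calendar need not. Chemotherapy may be given by a local oncologist (section 4.2.2), so an unambiguous written rule is worth having.

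There is a smaller data effect. Laboratory abnormalities that appear after radiation and resolve before cycle 2 may never be graded, and so would be missing from the toxicity tabulation (sections 10.2 and 12.5.2).

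**Working it through.** The plan states no figure for the age of a reused sample, so there is none to reproduce. The age follows from the plan's windows.

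**Inputs**

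- Blood draw to enrollment: 0 to 45 days (criterion 6).
- Eligibility determination to first fraction: 0 to 30 days (section 4.2). Eligibility is assumed to be determined on the day of enrollment.
- First to last fraction, assuming uninterrupted weekday treatment: 4 or 6 days for five fractions (the sixth may be omitted under section 4.2.1.2), and 7 days for six fractions, which must cross a weekend.
- Last fraction to cycle 1 day 1: 14 to 28 days (section 4.2), assumed to run from the last fraction.

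**Age of a reused sample at cycle 1** = the sum of the four intervals.

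- Minimum: 0 + 0 + 4 + 14 = 18 days.
- Maximum: 45 + 30 + 7 + 28 = 110 days.
- Every window at its midpoint (an illustration, not an observed value): 22.5 + 15 + 4 + 21 = 62.5 days, or 64.5 and 65.5 days with a radiation span of 6 or 7 days.
- If the 7-day schedule allowance in section 4.2.2.1 also applies to cycle 1: 18 − 7 = 11 days and 110 + 7 = 117 days.
- A radiation hold under section 6.2 would lengthen all of these.

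**First scheduled labs after radiation if the footnote is used** (cycle 2, before any 7-day shift)

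- 14-day regimens: 14 + 14 = 28 to 28 + 14 = 42 days after the last fraction.
- XELOX, 21-day cycle: 14 + 21 = 35 to 28 + 21 = 49 days.

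**Can a reused sample trigger a count-based delay?**

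| | Needed for eligibility (criterion 6) | Highest level at which section 6.1.1 advises delay |
|---|---|---|
| Neutrophils (per µL) | at least 1,500 | 1,200 |
| Platelets (per µL) | at least 100,000 | 75,000 |

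A sample that qualified the patient is above both delay levels. Reused at cycle 1, it can never lead to a count-based delay, so for that cycle the check has no content.

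**Why the remedy needs a window as well as a post-radiation requirement**

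A sample drawn the day after the last fraction is 28 − 1 = 27 days old if cycle 1 falls on day 28. With a 7-day window it is at most 7 days old and, on the nominal schedule, is drawn at least 14 − 7 = 7 days after radiation.

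**The case against.** The strongest reply is that the footnote permits reuse and does not require it. It sets a minimum research schedule, not the whole standard for releasing chemotherapy. Section 6.1 directs investigators to package inserts, local pharmacy practice and best practice, and leaves dose and schedule to the treating oncologist. It also says that results obtained before the "infusion should also be supplied in the patient study chart". A physician sees the patient once during radiation, adverse events are assessed in each cycle, and for patients treated locally section 7.2.3 says "they will have a televisit, over a secure server, before every cycle". All of this stands: cycle 1 is not given without clinical review, and any site may draw fresh labs. But none of these provisions requires a post-radiation count or limits the age of the sample, and a video visit cannot detect a low count that causes no symptoms.

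Second, a general rule with a footnoted exception is ordinary protocol structure. That is fair. The mismatch with section 7.2.3 is a missing cross-reference and would not matter much alone. The substance is what the exception allows.

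Third, the harm is hypothetical. The documents give no rate, grade or duration of cytopenia after short-course radiation, and section 7.1.5 lists no hepatic effect. The section 6.1 levels are recommendations. This stands as a limit on what can be claimed, and it makes the chemistry argument weaker than the count argument.

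Fourth, the extremes of the range are unlikely. The 18-day floor needs blood draw, enrollment and first fraction on one day, although CT-based planning and the section 4.1 assessments must come first. The 110-day ceiling needs every window at its limit. An 11-day age would breach the 2-week minimum gap in section 4.2, so 11 and 117 are conditional figures only. Even so, the most favorable case within the windows is more than two weeks old and predates radiation.

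Fifth, the stopping and acceptability rules in sections 12.2 and 12.7 count only non-hematologic toxicity of grade 4 or higher. A missed cytopenia therefore cannot change any decision in the trial. That is correct, and it is a reason to keep the rating low.

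**Conclusion.** The concern holds as a minor safety-monitoring point. Footnote i declares sufficient a sample that always predates radiation, that would be about 18 to 110 days old at cycle 1 (11 to 117 only if the 7-day allowance reaches cycle 1), and that cannot trigger the count-based delays in section 6.1.1. If it is used, no count or chemistry is scheduled after radiation until cycle 2.

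The range assumes same-day eligibility and enrollment, uninterrupted weekday radiation, and a gap counted from the last fraction. The conclusion that the sample predates radiation needs none of these assumptions, since it follows from the treatment order alone. How often sites use the allowance, and how often a patient would be harmed, cannot be judged from the documents. The sample size, the two-stage rule and the complete response analysis are unaffected. The data effect is limited to possible under-recording of post-radiation laboratory abnormalities.

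**What to change.** In footnote i, delete the clause that lets pre-study labs serve for cycle 1 day 1, and keep the CEA exemption. In its place require a blood count with differential and a chemistry panel that are drawn after the last radiation fraction, fall within a short stated window before cycle 1 day 1, and are reviewed before the infusion. Seven days is an example; the figure is for the investigator to set. The calendar and section 7.2.3 then agree.

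Keeping the footnote and adding only a maximum sample age is a lighter alternative. It closes the gap only if the limit also forces the draw to come after radiation.

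The cost is one footnote edit in the next amendment and one routine draw per patient, which section 7.2.3 already calls for. It can be combined with the post-radiation ctDNA draw (footnote k) only when that draw falls inside the stated window.
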